## Which IRB

 Medical  NonMedical

## Protocol Process Type

 Exemption  
 Expedited (Must be risk level 1)  
 Full

**IMPORTANT NOTE:** You will not be able to change your selections for "Which IRB" and "Protocol Process Type" after saving this section. If you select the wrong IRB or Protocol Process Type, you may need to create a new application.

See below for guidance on these options, or refer to ORI's "[Getting Started](#)" page. Please contact the Office of Research Integrity (ORI) at [contact] with any questions prior to saving your selections.

**\*Which IRB\***

The **Medical IRB** reviews research from the Colleges of:

- Dentistry
- Health Sciences
- Medicine
- Nursing
- Pharmacy and Health Sciences
- and Public Health.

The **Nonmedical IRB** reviews research from the Colleges of:

- Agriculture
- Arts and Sciences
- Business and Economics
- Communication and Information
- Design; Education
- Fine Arts
- Law
- and Social Work

**Note:** Studies that involve administration of drugs, testing safety or effectiveness of medical devices, or invasive medical procedures must be reviewed by the **Medical IRB** regardless of the college from which the application originates.

**\*Which Protocol Process Type\***

Under federal regulations, the IRB can process an application to conduct research involving human subjects in one of three ways:

- by exemption certification
- by expedited review.
- by full review;

The investigator makes the preliminary determination of the type of review for which a study is eligible. Please refer to ORI's "[Getting Started](#)" page for more information about which activities are eligible for each type of review.

The revised Common Rule expanded exemption certification category 4 for certain secondary research with identifiable information or biospecimens. The regulations no longer require the information or biospecimens to be existing. For more information see the [Exemption Categories Tool](#).

**PROJECT INFORMATION****0 unresolved  
comment(s)**

Title of Project: (Use the exact title listed in the grant/contract application, if applicable).

If your research investigates any aspect of COVID-19, please include "COVID19" at the beginning of your Project Title and Short Title

MCC-20-GI-114-PMC: Randomized, Parallel Arm, Phase II  
Study of Telotristat (Xermelo) in Combination with Lutetium  
Lu 177 Dotatate (Lutathera) in Well Differentiated  
Neuroendocrine Tumors (NETs)

**Short Title Description**

Please use a few key words to easily identify your study - this text will be displayed in the Dashboard listing for your study.

MCC-20-GI-114-PMC:Telotristat +  
Lutathera NET

Anticipated Ending Date of Research Project: 6/30/2034

Maximum number of human subjects (or records/specimens to be reviewed)

12

After approval, will the study be open to enrollment of new subjects or new data/specimen collection?  Yes  No

**RISK LEVEL****0 unresolved  
comment(s)**

Indicate which of the categories listed below accurately describes this protocol

- (Risk Level 1) Not greater than minimal risk
- (Risk Level 2) Greater than minimal risk, but presenting the prospect of direct benefit to individual subjects
- (Risk Level 3) Greater than minimal risk, no prospect of direct benefit to individual subjects, but likely to yield generalizable knowledge about the subject's disorder or condition.
- (Risk Level 4) Research not otherwise approvable which presents an opportunity to understand, prevent, or alleviate a serious problem affecting the health or welfare of subjects.

\*\*"Minimal risk" means that the probability and magnitude of harm or discomfort anticipated in the research are not greater in and of themselves from those ordinarily encountered in daily life or during the performance of routine physical or psychological examination or tests.

**\*\*\*For Expedited and Exempt Applications, the research activities must be Risk Level 1 (no more than minimal risk to human subjects).\*\*\***

Refer to [UK's guidance document](#) on assessing the research risk for additional information.

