**SUBJECT DEMOGRAPHICS**

0 unresolved comment(s)

Age level of human subjects: (i.e., 6 mths.; 2yrs., etc.)  to **Study Population:**

Describe the characteristics of the subject population, including age range, gender, ethnic background and health status. Identify the criteria for inclusion and exclusion.

Provide the following information:

- A description of the subject selection criteria and rationale for selection in terms of the scientific objectives and proposed study design;
- A compelling rationale for proposed exclusion of any sex/gender or racial/ethnic group;
- Justification for the inclusion of vulnerable groups such as children, prisoners, adults with impaired consent capacity, or others who may be vulnerable to coercion or undue influence.

Please consider these resources:

[NIH Diversity Policy](#)

[FDA Diversity Guidance](#) 

Study Population: A description of the subject selection criteria and rationale for selection in terms of the scientific objectives and proposed study design: The inclusion criteria are based on the requirements for patient selection needed to achieve the primary objectives of the study. See attached eligibility criteria. Subject must be 18 years of age or older. The racial composition will reflect the population of Central Kentucky and the patients seen at the Markey Cancer Center: Caucasian: African American: Hispanic: Asian:Native American: 70:20:10:<1:<1 %.

- A compelling rationale for proposed exclusion of any sex/gender or racial/ethnic group: No groups are excluded from this study.
- The proposed dates of enrollment (beginning and end): We expect to enroll 70 patients in 30 months.
- A description of proposed outreach programs for recruiting women and minorities in clinical research as subjects: Only the IRB approved procedures in place as described in the "Subject Recruitment Methods & Privacy" section will be used.
- The proposed dates of enrollment will be from 9/1/2020 through 6/30/2034.

See Appendix Eligibility for additional information.

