#### Sample Size/Accrual Rate

A sample of 33 patients per arm will provide 80% power to test a non-inferiority difference of 5% for the combination based on a one-sided test with 5% significance level. Based on the NETTER trial [7], we will assume that PFS rate at 20 months is equal to 65%. We will further assume a small non-inferiority margin of 5% and that the PFS at 20 months with the PRRT (Lutathera)+Telotristat combination is equal to 80%. The assumption in hypothesized effect size of the combination is based on the width of the 95% confidence interval presented in the NETTER trial results. If at least 25 out of 33 patients in each arm progression-free at 20 months, we will conclude that PFS rate at 20 months for the combination (either arm) is non-inferior. To account for a potential 5% drop-out/non-evaluable rate, we will enroll 35 patients per arm. We expect to enroll 2-3 patients per month. Thus, a total of 70 patients requires an accrual duration approximate of 30 months (2.5 years) and study duration approximate of 66 (5.5 years) months (30 months accrual plus 36 months follow-up).

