#### Randomization and Stratification

Permuted block randomization will be generated with a 1:1 allocation ratio for the two treatment arms. A separate randomization list will be generated to account for the stratification factor of tumor grade (Grade 1 and 2). The study statistician will generate the randomization list and incorporated into the clinical trial management system.

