- Failure to comply with AE/SAE reporting requirements
- poor study enrollment
- protocol violations, or issues related to patient safety

[Back to Top](#)

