### 9.2 Sample Size/Accrual Rate

A sample of 33 patients per arm will provide 80% power to test a non-inferiority difference of 5% for the combination based on a one-sided test with 5% significance level. Based on the NETTER trial [7], we will assume that PFS rate at 20 months is equal to 65%. We will further assume a small non-inferiority margin of 5% and that the PFS at 20 months with the PRRT (Lutathera)+Telotristat combination is equal to 80%. The assumption in hypothesized effect size of the combination is based on the width of the 95% confidence interval presented in the NETTER trial results. If at least 25 out of 33 patients in each arm progression-free at 20 months, we will conclude that PFS rate at 20 months for the combination (either arm) is non-inferior. To account for a potential 5% drop-out/non-evaluable rate, we will enroll 35 patients per arm. We expect to enroll 2-3 patients per month. Thus, a total of 70 patients requires an accrual duration approximate of 30 months (2.5 years) and study duration approximate of 66 (5.5 years) months (30 months accrual plus 36 months follow-up)

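### The application enters 12 as the maximum number of subjects while the rest of the plan enrols 70, and nothing readable reconciles the two

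*Combined protocol and SAP*

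**What the plan says.** Four places state a study size.

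- **Project Information (printed under Short Title Description).** The field "Maximum number of human subjects (or records/specimens to be reviewed") carries the value 12 on the next line.
- **Subject Demographics, Study Population.** "We expect to enroll 70 patients in 30 months". This gives a total only, with no per-arm figure.
- **Research Description, Sample Size/Accrual Rate.** 33 evaluable and 35 enrolled per arm, and then: "Thus, a total of 70 patients requires an accrual duration approximate of 30 months".
- **Section 9.2.** The same text again. It ties 80% power to 33 patients per arm, sets the decision rule ("If at least 25 out of 33 patients in each arm progression-free at 20 months") and allows for drop-out ("we will enroll 35 patients per arm").

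Sections 9.1 and 9.5 plan no interim analysis. Section 9.6 specifies 1:1 permuted blocks without a block size, and adds: "A separate randomization list will be generated to account for the stratification factor of tumor grade (Grade 1 and 2").

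**The concern.** A trial with a ceiling of 12 cannot enrol 70, so at least one of these numbers does not describe the current plan. What is at stake depends on which one is wrong. If 70 is the plan, the maximum put before the review board is too low and the repair is clerical. If 12 is the plan, the power statement and the decision rule of the only primary hypothesis test describe a trial that is not being run. A report that kept that wording would then claim more than 12 patients can show.

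**Working it through.** **Inputs, from sections 9.2 and 9.3.** Historical 20-month PFS rate 65%; non-inferiority margin 5 percentage points; assumed true rate 80%; one-sided 5% level; exact one-proportion test in each arm separately; 5% drop-out.

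**Step 1: reproduce the plan's own figure.**
- Null rate: 0.65 − 0.05 = 0.60.
- Size of the rule: P(X ≥ 25 | n = 33, p = 0.60) = 0.0444, which is within 5%.
- One success fewer: P(X ≥ 24 | n = 33, p = 0.60) = 0.0923, which is too large. So 25 is the correct cut-off.
- Power: P(X ≥ 25 | n = 33, p = 0.80) = 0.79996, or 80.0%.
- Drop-out: 33 / 0.95 = 34.7, rounded up to 35 per arm; 2 × 35 = 70.
- Accrual: 70 / 30 = 2.33 per month, inside the stated 2 to 3.

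The 70-patient plan is therefore correct and consistent with itself.

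**Step 2: size of the mismatch.** 70 − 12 = 58 subjects, and 12 / 70 = 17%. Twelve is also below the 33 evaluable patients needed in a single arm.

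**Step 3: what would follow only if 12 governs.** Take the planned 1:1 allocation with all 12 patients evaluable, so 6 per arm.
- 25 progression-free patients in an arm is impossible.
- The exact one-sided 5% rule against 60% becomes 6 of 6. Its size is 0.60^6 = 0.0467.
- Power at a true rate of 80% is 0.80^6 = 0.262, about 26%, against the stated 80%.
- With 5 evaluable patients in an arm, even 5 of 5 has size 0.60^5 = 0.078, above 5%. With fewer patients the size is larger still. No valid rule exists at 5 or below.

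Section 9.3 treats patients not evaluated at 20 months as non-evaluable, so under a 6:6 split one such patient would leave that arm without a rule. An exact 6:6 split is itself not assured, because block size is unstated and the lists are separate by grade.

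**Step 4: look for an explanation of the 12.**
- *Specimens or records:* the field label also covers these, but this is a randomised treatment trial, and the Records, Privacy, and Confidentiality section says no research specimens are collected.
- *Planned early stop:* ruled out for the primary endpoint, since no interim analysis is planned.
- *Suspension of accrual:* Data and Safety Monitoring lists "poor study enrollment" among the grounds, but no section says this happened.
- *Enrolment status:* the question printed right after the 12 asks whether the study will be open to new enrolment. Its tick-box answer cannot be read in the available text.

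**The case against.** The strongest reply is that 12 is a single entry in an administrative form. No hypothesis, rule or analysis in section 9 uses it. The primary test rests on 33 per arm, which is correctly derived; the two copies of the sample-size text agree, and Subject Demographics matches their total. The unreadable answer about open enrolment might explain the 12, and its absence from the available text is not a gap in the plan. All of this stands. It limits the point to a conflict to be reconciled and makes the power consequences conditional.

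It does not remove the conflict. Both numbers are printed in current text, and no readable statement says that one replaces the other. The enrolment end date of 6/30/2034 does not settle the matter either.

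A reader might go further and infer that the trial was cut to 12, or closed after 12, and that its primary test is therefore underpowered. The documents do not support this: they record no reduction, closure or actual accrual, and an entry error fits the text equally well. Nor is it useful to tabulate power for every uneven split of 12. Those splits depend on an unstated block size, and many are remote under 1:1 blocked allocation.

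**Conclusion.** The mismatch is certain. The application's maximum is 12, the plan elsewhere is 70, and the documents do not say which governs. It should be fixed, but it is not a defect in the sample-size derivation, and no effect on the primary test has been shown. The loss of power from 80% to about 26% per arm holds only if 12 governs, allocation is exactly 6:6, all 12 patients are evaluable and the true 20-month rate is 80%. Confidence is high for the conflict between the two numbers and does not extend to those consequences.

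**What to change.** State which number governs, and align the Project Information entry, Subject Demographics, the Research Description and section 9.2.

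- **If 70 governs:** correct the Project Information entry. Section 9.2 needs no change on this point. The cost is one corrected field, which puts 58 more subjects before the review board than are now entered, although 70 is already the number planned elsewhere.
- **If 12 governs:** add a short dated note to the application and section 9 giving the reduction and its reason. Keep the 33-per-arm design only as the superseded plan. State that the 80% power and the 25-of-33 rule no longer apply. Report 20-month PFS in each arm as an estimate with a 95% confidence interval, and draw no powered non-inferiority conclusion.

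Neither route asks for patients beyond the number that governs.

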**SUBJECT DEMOGRAPHICS**

0 unresolved comment(s)

Age level of human subjects: (i.e., 6 mths.; 2yrs., etc.)  to **Study Population:**

Describe the characteristics of the subject population, including age range, gender, ethnic background and health status. Identify the criteria for inclusion and exclusion.

Provide the following information:

- A description of the subject selection criteria and rationale for selection in terms of the scientific objectives and proposed study design;
- A compelling rationale for proposed exclusion of any sex/gender or racial/ethnic group;
- Justification for the inclusion of vulnerable groups such as children, prisoners, adults with impaired consent capacity, or others who may be vulnerable to coercion or undue influence.

Please consider these resources:

[NIH Diversity Policy](#)

[FDA Diversity Guidance](#) 

Study Population: A description of the subject selection criteria and rationale for selection in terms of the scientific objectives and proposed study design: The inclusion criteria are based on the requirements for patient selection needed to achieve the primary objectives of the study. See attached eligibility criteria. Subject must be 18 years of age or older. The racial composition will reflect the population of Central Kentucky and the patients seen at the Markey Cancer Center: Caucasian: African American: Hispanic: Asian:Native American: 70:20:10:<1:<1 %.

- A compelling rationale for proposed exclusion of any sex/gender or racial/ethnic group: No groups are excluded from this study.
- The proposed dates of enrollment (beginning and end): We expect to enroll 70 patients in 30 months.
- A description of proposed outreach programs for recruiting women and minorities in clinical research as subjects: Only the IRB approved procedures in place as described in the "Subject Recruitment Methods & Privacy" section will be used.
- The proposed dates of enrollment will be from 9/1/2020 through 6/30/2034.

See Appendix Eligibility for additional information.

**Attachments**

Attach Type	File Name
StudyPopulation	Appendix eligibility.pdf

Indicate the targeted/planned enrollment of the following members of minority groups and their subpopulations. Possible demographic sources: [Census Regional Analyst Edition](#), [Kentucky Race/Ethnic Table](#), [Kentucky Population Data](#).

(Please note: The IRB will expect this information to be reported at Continuation Review time for Pre-2019 FDA-regulated Expedited review and Full review applications):

Participant Demographics				
	Cisgender Man 	Cisgender Woman 	TGNB/TGE 	Unknown/Not Reported
American				
Indian/Alaskan Native:				
Asian:				
Black/African American:				
Latinx:				
Native Hawaiian/Pacific Islander:				
White:				
American Arab/Middle Eastern/North African:				
Indigenous People Around the World:				
More than One Race:				
Unknown or Not Reported:				

If unknown, please explain why:

The racial composition will reflect the population of Central Kentucky and the patients seen at the Markey Cancer Center: Caucasian: African American: Hispanic: Asian: Native American: 70:20:10:<1:<1 %.

Indicate the categories of subjects and controls to be included in the study. You may be required to complete additional forms depending on the subject categories which apply to your research. If the study does not involve direct intervention or direct interaction with subjects, (e.g., record-review research, outcomes registries), do not check populations which the research does not specifically target. For example: a large record review of a diverse population may incidentally include a prisoner or an international citizen, but you should not check those categories if the focus of the study has nothing to do with that status.

Check All That Apply (at least one item must be selected)

**ADDITIONAL INFORMATION:**

- Children (individuals under age 18)
- Wards of the State (Children)
- Emancipated Minors
- Students
- College of Medicine Students
- UK Medical Center Residents or House Officers
- Impaired Consent Capacity Adults
- Pregnant Women/Neonates/Fetal Material
- Prisoners
- Non-English Speaking (translated long or short form)
- International Citizens
- Normal Volunteers
- Military Personnel and/or DoD Civilian Employees
- Patients
- Appalachian Population

Please visit the [IRB Survival Handbook](#) for more information on:

- Children/Emancipated Minors
- Students as Subjects
- Prisoners
- Impaired Consent Capacity Adults
- Economically or Educationally Disadvantaged Persons

Other Resources:

- UKMC Residents or House Officers [see [requirement of GME](#)]
- [Non-English Speaking](#) [see also the E-IRB Research Description section on this same topic]
- [International Citizens](#) [DoD SOP may apply]
- [Military Personnel and/or DoD Civilian Employees](#)

**Assessment of the potential recruitment of subjects with impaired consent capacity (or likelihood):**

Check this box if your study does NOT involve direct intervention or direct interaction with subjects (e.g., record-review research, secondary data analysis). If there is no direct intervention/interaction you will not need to answer the impaired consent capacity questions.

Does this study focus on adult subjects with any conditions that present a high *likelihood* of impaired consent capacity or *fluctuations* in consent capacity? (see examples below)

Yes  No

If Yes and you are not filing for exemption certification, go to ["Form T"](#), complete the form, and attach it using the button below.

**Examples of such conditions include:**

- Traumatic brain injury or acquired brain injury
- Severe depressive disorders or Bipolar disorders
- Schizophrenia or other mental disorders that involve serious cognitive disturbances
- Stroke
- Developmental disabilities
- Degenerative dementias
- CNS cancers and other cancers with possible CNS involvement
- Late stage Parkinson's Disease
- Late stage persistent substance dependence
- Ischemic heart disease
- HIV/AIDS
- COPD
- Renal insufficiency
- Diabetes
- Autoimmune or inflammatory disorders
- Chronic non-malignant pain disorders
- Drug effects
- Other acute medical crises

Attachments

## INFORMED CONSENT/ASSENT PROCESS/WAIVER

1 unresolved  
comment(s)

For creating your informed consent attachment(s), please download the most up-to-date version listed in "All Templates" under the APPLICATION LINKS menu on the left, and edit to match your research project.

Additional Resources:

- [Informed Consent/Assent Website](#)
- [Waiver of Consent vs. Waiver of Signatures](#)
- [Sample Repository/Registry/Bank Consent Template](#)

**Consent/Assent Tips:**

- If you have multiple consent documents, be sure to upload each individually (not all in a combined file).
- If another site is serving as the IRB for the project, attach the form as a "Reliance Consent Form" so the document will not receive a UK IRB approval stamp; the reviewing IRB will need to stamp the consent forms.
- Changes to consent documents (e.g., informed consent form, assent form, cover letter, etc...) should be reflected in a 'tracked changes' version and uploaded separately with the Document Type "Highlighted Changes".
- It is very important that only the documents you wish to have approved by the IRB are attached; DELETE OUTDATED FILES -- previously *approved* versions will still be available in Protocol History.
- Attachments that are assigned a Document Type to which an IRB approval stamp applies will be considered the version(s) to be used for enrolling subjects once IRB approval has been issued.

Document Types that do NOT get an IRB approval stamp are:

- "Highlighted Changes",
- "Phone Script", and
- "Reliance Consent Form",
- "Sponsor's Sample Consent Form".

**How to Get the Section Check Mark**

1. You must:
  - a) provide a response in the text box below describing how investigators will obtain consent/assent, and
  - b) check the box for at least one of the consent items and/or check mark one of the waivers
2. If applicable attach each corresponding document(s) **as a PDF**.
3. If you no longer need a consent document approved (e.g., closed to enrollment), or, the consent document submitted does not need a stamp for enrolling subjects (e.g., umbrella study, or sub-study), only select "Stamped Consent Doc(s) Not Needed".
4. After making your selection(s) be sure to scroll to the bottom of this section and **SAVE** your work!

